## **RESEARCH PROTOCOL SUMMARY**

TITLE:	Prospective Evaluation of Applied 'Lite' Compression for leg ulcer Healing, a pragmatic multi-centre randomized controlled trial
Short title:	PEACH trial
IRAS number	280418
Device description	Andoflex ™ TLC Calamine Lite Two-Layer Compression System.
	
 
Compression of ('Lite' compression) 20-30 mmHg, primarily intended for patients with an ABPI of 0.5 to 0.8. Layer 1 is a soft foam roll impregnated with calamine that is designed to soothe and calm skin with multiple wounds or other skin conditions. Layer 2 is a short stretch compression bandage that sticks to itself and features Easy HandTear Technology. Absorbs 20xs its dry weight vs. traditional Unna Boot, and contains 50% more active ingredients than traditional Unna Boot. It provides a two-step short stretch performance with high working pressure and low resting pressure. Visual indicators are provided for ease of application - ovals become circles when the intended compression System
 
3M™ Coban™ 2 Lite Two-Layer Compression System
 
This provides ('Lite' compression) 25-30 mmHg compression, primarily intended for patients with ABPI 0.5 – 0.8. Coban 2 Lite Layer Compression Systems are indicated for the treatment of venous leg ulcers, lymphedema and other conditions where compression is appropriate, such as post-operatively.
 
Each of the above systems is supplied as a kit that includes two rolls: a Comfort Layer roll and a Compression Layer roll. They
 

	have been shown to provide sustained therapeutic compression for up to 7 days.
Study design	Multi-centre, controlled, prospective randomized non- inferiority trial
Primary objective	To determine the relative efficacy of two-layer Lite compression bandaging for the management of leg ulcers, measured through wound status (healed vs non-healed) at 12 weeks post-baseline

Secondary objectives	
 
To determine the efficacy of two-layer Lite compression bandaging for the management of leg ulcers at 6 and 12 weeks post-baseline
 
Wound status (healed vs non-healed at 6 weeks)
 
Healing rate (ulcer size, PUSH score)
 
Quality of Life (EQ-5D-5L)
 
Leg ulcer related quality of life score (VEINES-QoL)
 
Leg ulcer related pain and pruritus levels
 
Infection rates, withdrawal rates
 

Patient population	
 
Pragmatic approach to allow inclusion of wider cohort of patients than those with pure venous leg ulcers (VLU).
 
Therefore, patients with leg ulcer who are suitable for reduced (ie 'Lite') compression are considered for inclusion.
 
Specifically, these are: 
 
VLU
 
Mixed venous and arterial leg ulcers
 
 
 
Suitability for reduced compression is an ABPI of 0.5 -0.8 depending on holistic assessment. ABPI measured within last 3 months is part of the decision making to use reduced (Lite) rather than full compression. Only if ABPI or other diagnostic method (eg pulse palpation and ultrasound diagnostics, toe pressure assessment or arterial imaging) is not available or applicable then provision of solely a clinical assessment is allowed.
 

Sample size	
 
A total of 92 participants, over the age of eighteen, with leg ulcers. Power beta of 80%, one-sided alpha p-value of 0.025, non-inferiority limit 15%. Assumption of 15% difference in absolute percentage healed ulcers in intervention (Andoflex) arm versus control (Coban2) arm.
 
Therefore, 97.5% confidence interval for Andoflex to be no more than 15% worse than mean ulcers healed percentage for Coban2.
 
Sample size with 10% attrition rate included: 92 patients Of which: 
 
46 Patients to receive Andoflex TLC Calamine Lite
 
46 Patients to receive Coban2 Lite
 
 
 
Participants must have the capacity to provide informed written consent and complete patient reported outcome measures. Participants are recruited from the local community nursing caseload and identified in hospital clinics.
 

	Randomisation will be stratified for ulcer size, with cut-off	
	PUSH score of up to and including 10, or 11 and above.	
Sponsor	North Cumbria Integrated Care NHS Foundation Trust	
5001301	North Cumbra integrated care with roundation must	
Manufacturer & funder	Milliken Healthcare Inc	
	UK-based contact: [name], Clinical Specialist EMEA ,	
	Milliken Healthcare Division, [name] ,	
	[contact]	
Chief Investigator	[name], vascular specialist nurse, Vascular Surgery	
	Dept, North Cumbria University Hospitals NHS Trust.	
	[contact]	
Co-investigators	[name] PhD, Research Project Lead, [contact];	
	Cumbria Partnership NHS Foundation Trust	
	R&D Department, Carleton Clinic	
	[name]	
	[contact]	
	[name], GPwSI Research, Cumbria Partnership NHS	

#### 1. LAY SUMMARY

Leg ulcers are a challenging condition to manage and treat; there is a high risk of the wounds becoming chronic, infected and needing surgical intervention. Apart from having a significant negative impact on patients' lives, it is also an economic burden to the National Health Service. Compression bandaging is the main treatment option for leg ulcers, and patient compliance with this therapy is key to maximise chances of wound healing and minimise the risk of complications. In recent years, compression bandaging has become more functional and comfortable for patients, but in a recent study we showed that itching and other undesirable symptoms related to having a leg bandaged are still an issue. Initial data has demonstrated that a novel bandage called Andoflex TLC Calamine (Milliken Healthcare Inc) reduces discomfort and possibly accelerates leg ulcer healing. In this pragmatic randomised controlled trial, leg ulcer patients who may benefit from reduced compression therapy will be allocated by chance to one of two bandages: Andoflex TLC Calamine Lite or 3M's Coban 2 Lite. The aim is to determine how effective each bandage is at promoting leg ulcer healing over a period of 12 weeks. In total, 92 patients are planned to be enrolled and for clinical reasons these patients cannot be administered full compression bandaging and are hence administered reduced (or 'Lite') compression bandaging. Outcome measures will be wound healing rates and also patient reported quality of life.

#### 2. INTRODUCTION

Leg ulcers can occur for various reasons, see Figure 1. Though venous leg ulcers (VLUs) are the most common type of leg ulcers, contributing to the majority of leg ulcers, there are many patients who have ulcers due to a mixed venous-arterial or other underlying condition (SIGN 2010, Graham *et al* 2003). The natural history of the disease – particularly in those patients who have venous insufficiency and or other chronic disease affecting the vasculature such as diabetes and peripheral arterial disease - is a continuous cycle of healing and breakdown over decades. VLUs are associated with considerable expense, morbidity and impaired quality of life (Persoon *et al* 2004). A positive relationship has been observed between VLU occurrence and specific modern lifestyle risk factors such as sedentary lifestyles and obesity (Brand *et al* 1998). Table 1 shows annual NHS cost for treating VLUs compared to other chronic wound treatments.

	Annual incidence	Cost per patient	Annual NHS cost (2005–2006)
Venous leg ulcers	108,600	£1,500-1,800	£168–198m
Foot ulcers	57,000	£5,200	£300m
Pressure ulcers	410,000	£4,300-6,400	£1.8-2.6bn
TOTAL	575,600	£4,000-5,400	£2.3-3.1bn

#### Table 1. Chronic wound treatment costs to the NHS (Posnett & Franks 2008)

	Venus
Vascular	Arterial
	Mixed
	Diabetes
Neuropathic	Tabes
	Syringomyelia
	Diabetes
Metabolic	Gout
	Prolidase deficiency
Usemetalogical	Sickle cell disease
Haematological	Cryoglobulinemia
	Pressure
Trauma	Injury
	Burns
Tumors	Basal cell carcinoma
Tumors	Squamous cell carcinoma
	Bacterial
Infection	Fungal
	Protozoal
Panniculitis	Necrobiosis lipoidica
Panniculius	Fat necrosis
Pyoderma	Gangrenosum
Special	Hypertensive ulcer

#### Figure 1, Different causes of leg ulcers (Agale 2013)

Despite extensive research the exact manner in which particularly venous leg ulcers develop, is not yet fully understood however it is agreed that prolonged venous hypertension caused by chronic venous insufficiency is a common aetiological factor (Eberhardt & Rafetto 2005, White & Ryjewski 2005). The mainstay of treatment of leg ulcers is compression bandaging (O'Brien *et al* 2012), however up to 15-30% do not respond to this current gold standard treatment and remain unhealed even after 6 months of treatment (Moffett *et al* 2006, O'Meara, Cullum & Nelson 2009). Depending on the degree of venous insufficiency, any arterial impairment and other clinical and patient-specific factors, the applied compression can be as high as 40 mmHg. Since many patients' leg ulcer pathologies are not suitable to receive full compression, there is paucity in evidence managing leg ulcers with reduced compression bandaging (20-30 mmHg).

The first 'gold' standard bandaging for chronic venous insufficiency (CVI) was Unna's boot, though the application of bandaging and other products goes back thousands of years (Rubin et al, 1990; Thomas , 1997). This concerned a gauze dressing impregnated with Zinc oxide and calamine lotion. The bandaging was then further developed to be elasticated and provide better compression, for a time using four layers around the leg. The modern compression bandaging products (incl Coban2 and OptiFlex) are two-layer short stretch compression bandaging systems (Hanna et al , 2008). Milliken Healthcare Inc has combined one of the elements of Unna's boot, namely the skin soothing ingredients Zinc Oxide (ZnO) and Calamine, and the favoured two-layer design. One of the Milliken products contains ZnO (Andoflex Zn) and the other Calamine (Andoflex TLC Calamine).

Treatment success in CVI is highly dependent on achieving high levels of patient compliance. Unfortunately, compliance rates are often poor in this population (Heinen et al , 2007). Undesirable effects of compression bandaging play a role in this. Apart from bandage slippage, the most common undesirable effects of wearing compression bandaging are skin-related. Dryness and redness of the skin are commonly reported, and pruritus develops in as many as 1 in 3 patients (Reich-Schupke et al, 2009). Unna's boot has been shown in the past to be effective at controlling pruritis in different conditions, including burns-related long-term itch (Shohrati et al, 2007). A recent study by Jonker and colleagues (2020) showed that patients deem the Andoflex TLC Calamine compression bandaging more comfortable, and less itchy, than Coban2 compression bandaging; there was also a trend towards improved healing rates with Andoflex TLC Calamine.

The aim of this pragmatic randomised, controlled, prospective trial is to determine the efficacy of two types of two-layer compression bandaging (Andoflex TLC Calamine Lite and Coban 2 Lite), with a primary outcome measure of healed ulcer at week 12. Secondary outcome measures will be other ulcer characteristics, and patient-reported quality of life.

## 3. INVESTIGATIONAL DEVICES

Two different two-layer compression bandages will be appraised. Apart from Andoflex TLC Calamine Lite, provided free of charge by Milliken Healthcare Inc as part of the non-restricted research grant for this study, the other bandage (Coban 2 Lite) will be purchased by the relevant healthcare provider via the conventional Trust NHS supply chain. Coban 2 is a first-line product listed in North Cumbria Integrated Care NHS Trust's current formulary (Appendix 3). Therefore, Coban2 Lite effectively is the treatment as usual arm.

## 3.1 Andoflex TLC Calamine Lite

Full product information on the Andoflex TLC Calamine 2-layer compression system can be found on the Milliken Healthcare Inc website https://andoverhealthcare.com/product/Andoflex-tlc-calamine/. Andoflex® TLC Calamine (known as AndoFlex® TLC Calamine in the UK) is manufactured by and is a registered trademark of Andover Healthcare, Inc., a subsidiary of Milliken Healthcare Products, LLC

There are two pressure options, with the Lite version applied in this trial: compression of either (standard compression) 35-40 mmHg or ('Lite' compression) 20-30 mmHg, for patients with an ABPI of  $\geq 0.8$  or  $\geq 0.5$  respectively. Layer 1 is a soft foam roll impregnated with calamine that is designed to soothe and calm skin with multiple wounds or other skin conditions. Layer 2 is a non-latex short stretch compression bandage that sticks to itself and features Easy Hand Tear Technology, eliminating the need for scissors. Absorbs 20xs its dry weight vs. traditional Unna Boot, and 50% more active ingredients than traditional Unna Boot. It provides a two-step short stretch performance with high working pressure and low resting pressure. Visual indicators are provided for ease of application - ovals become circles when the intended compression is achieved.

## 3.2 Coban 2 Lite

Full product information on the 3M Coban 2-layer compression system can be found on the 3M website: https://www.3m.com/3M/en\_US/company-us/all-3m-products/~/3M-Coban-2-Layer-Compression-System?N=5002385+3293321927&rt=rud

From the literature: the product provides sustained therapeutic compression for up to 7 days, and it is clinically proven to significantly reduce slippage, to encourage longer wear. The compression layer is designed to be applied at full stretch, reducing application variability.

• Enables a more normal lifestyle – The thin, lightweight, breathable sleeve allows patients to wear their own shoes, so they can return to their regular daily activities

- Easy to use Application is fast, and easy to teach and learn.
- Not made with natural rubber latex

Engineered with Intelligent Compression Dynamics to stay in place and deliver comfortable, effective, therapeutic compression for venous leg ulcers and other conditions requiring compression

Again, there are two pressure options with the Lite version used in this trial: either (standard) 35-40 mmHg or ('Lite' compression) 25-30 mmHg compression, for patients with ABPI  $\geq 0.8$  or  $\geq 0.5$  respectively This provides 25-30 mmHg compression for patients with ABPI greater than or equal to 0.5. Coban2 Layer Compression Systems are indicated for the treatment of leg ulcers, lymphedema and other conditions where compression is appropriate, such as post-operatively. Each system is supplied as a kit that includes two rolls: a Comfort Layer roll and a Compression Layer roll.

# 3.3 Medical Device management and use of different compression bandage brands

Bandages will be stored in the clinic rooms at the temperature recommended by the respective manufacturers. No requirement for involvement pharmacy or clinical trials pharmacist. Standard available stocks of dressings to be used, including Andoflex TLC Calamine provided free of charge by Milliken Healthcare Inc as part of the research grant.

## 4. STUDY HYPOTHESIS

#### 4.1 Primary objective

To determine the efficacy of two-layer Lite compression bandaging for the management of leg ulcers, measured through wound status (healed vs non-healed) at 12 weeks post-baseline

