#### 4.2 Secondary objective

To determine the efficacy of two-layer Lite compression bandaging for the management of leg ulcers at 6 and 12 weeks post-baseline

- Wound status (healed vs non-healed at 6 weeks)
- Healing rate (ulcer size, PUSH score)
- Leg ulcer related quality of life score (VEINES-QoL)

- Leg ulcer related pain and pruritus levels
- Generic quality of Life (EQ-5D-5L)

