#### 7. SAFETY

#### 7.1 Potential risks & benefits to study participants

There is no anticipated personal safety risk associated with taking part in this study. If the research team learns of important new information that might affect patient's desire to remain in the study, he or she will be told. Appropriate precautions are in place to ensure medical and personal information is kept safe through adhering to appropriate governance regulations. Participants in both the treatment arms will be allocated a compression bandage that is used for its intended licensed purpose and that is available via standard care routes. Any adverse events will be recorded, as outlined in sections below.

Apart from being allocated to a different type of compression bandage, all patients will be commenced on a compression therapy that aims to achieve 20-30 mmHg of pressure; therefore, all patients will receive the indicated clinical care they would receive when not in the trial too. They will otherwise be cared for in exactly the same manner as they normally would. Some bandage types may be more comfortable and more effective at controlling symptoms associated with vascular pathology and this present trial aims to establish whether this holds true. Participants cannot claim payments, reimbursement of expenses or any other benefits or incentives for taking part in this research.

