## 8.3 Secondary outcome statistics

To evaluate the effect of the different reduced compression bandages on leg ulcer healing, data from the two treatment arms will be compared.

Ulcer healing and more general health measures is assessed by the following parameters:

- Ulcer status (healed vs non-healed)
- Ulcer size (cm^2, measured with wound grid)
- PUSH score
- Visual analogue pain score
- Visual analogue pruritus score
- VEINES-QoL
- EQ-5D-5L

To assess the Ulcer size, PUSH score, visual analogue pain score, and visual analogue pruritus score, which are measured every 6 weeks, per treatment arm the average difference between time points will be calculated per treatment group (Wilcoxon test). To compare between the groups, Mann-Whitney U-test will be applied.

To measure patient-reported outcome measures on quality of life (VEINES-QoL and EQ-5D-5L) at baseline, week6 and week 12; the Wilcoxon test will be applied within treatment arms (over time) whereas the Mann-Whitney U-test will be performed between treatment arms. Data of the two treatment arms will be compared by applying the Mann-Whitney U-test.

Subject to sufficient data being available, Cox proportional hazards regression analysis will be conducted to investigate the role of the compression bandage itself and other covariates in leg ulcer healing rates. Other covariates include: leg ulcer size and chronicity at baseline, patient age, ulcer aetiology (pure venous vs other), absence/presence of co-morbidities, ulcer location, history of recurrent ulcers.

The following descriptive statistics will be reported on where possible:

- Number of patients screened
- Number of patients eligible/ineligible, and percentage of patients consented into the trial
- Number of patients completed the trial/discontinued (plus reasons if discontinued)

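### Sections 4.1 and 4.2 ask for the efficacy of Lite compression, which both arms receive; the design answers only the comparison of bandages, and the within-arm tests in 8.3 add no evidence on efficacy

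*Protocol*

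**What the plan says.** **Objectives.** Section 4 is headed as the study hypothesis, but it contains no comparator, margin or non-inferiority statement. Section 4.1 reads "To determine the efficacy of two-layer Lite compression bandaging for the management of leg ulcers, measured through wound status", judged at week 12. Section 4.2 reads "To determine the efficacy of two-layer Lite compression bandaging for the management of leg ulcers at 6 and 12 weeks post-baseline". The protocol summary words the primary objective differently: "To determine the relative efficacy of two-layer Lite compression bandaging for the management of leg ulcers". The introduction (Section 2) gives the aim as "to determine the efficacy of two types of two-layer compression bandaging" and names both products.

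**Treatment.** Section 7.1 says that "all patients will be commenced on a compression therapy that aims to achieve 20-30 mmHg of pressure". Section 3 says of the control: "Therefore, Coban2 Lite effectively is the treatment as usual arm". No arm goes without Lite compression.

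**Analysis.** Section 8.2 tests the primary outcome between arms only, by a confidence interval for the difference in proportions healed against a 15-point margin and by a chi-squared test. Section 8.3 assigns Wilcoxon tests between time points, per arm, to ulcer size, PUSH, pain and pruritus. For VEINES-QoL and EQ-5D-5L it states that "the Wilcoxon test will be applied within treatment arms (over time"). Each of these six outcomes also has a between-arm Mann-Whitney test.

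**The concern.** An objective fixes what a trial may conclude. As worded in 4.1 and 4.2, it asks whether Lite compression works. That needs patients who do not receive Lite compression, or a well-supported figure for how they would fare. The trial has no such patients, and the introduction says that "there is paucity in evidence managing leg ulcers with reduced compression bandaging".

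The within-arm tests in 8.3 are the only planned analyses that look like an answer to that literal question. They compare each arm with its own baseline. Every participant enters with an open ulcer, standard wound care continues throughout (5.4), and patients may already be on compression at entry (6.2.1). Change from baseline therefore mixes any bandage effect with natural course, routine care and regression to the mean. A report that followed Section 4 to the letter could present a small within-arm p-value as evidence that a bandage reduces ulcer size, pain or itch. Nothing in 8.3 marks these tests as descriptive.

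**Working it through.** **1. What the trial is sized for.** Inputs from Section 6.1: 65% healed with Andoflex, 50% with Coban 2, margin 15 points, one-sided alpha 0.025, power 80%.

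n per arm = (1.960 + 0.842)² × [0.50 × 0.50 + 0.65 × 0.35] / (0.15 + 0.15)² = 7.849 × 0.4775 / 0.09 = 41.6, so 42 per arm and 84 in total.

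Adding 10% gives 84 × 1.1 = 92.4, which matches the stated 92. (Dividing by 0.9 would give 94.) The stated figure reproduces as a between-arm calculation, so the design is built for a comparative question.

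**2. Question against design.**

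| Place | Question posed | Answerable with two Lite arms? |
|---|---|---|
| 4.1, 4.2 | Efficacy of Lite compression | No |
| Summary, primary objective | Relative efficacy | Yes |
| 6.1 | Non-inferiority, 15-point margin | Yes |
| 8.2 | Difference in proportion healed | Yes |
| 8.3, Mann-Whitney | Difference between arms | Yes |
| 8.3, Wilcoxon | Change from an arm's own baseline | Describes change; gives no cause |

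**3. How many within-arm tests.** Six outcomes × 2 arms × 2 follow-up visits (weeks 6 and 12) = 24, if each visit is compared with baseline.

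**4. What a within-arm test shows when the arms do not differ.** This is a simulation for ulcer area only. The protocol gives no distribution of ulcer size or change, so all of the following is assumed:

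- 41 patients per arm (46 × 0.9 = 41.4).
- Baseline area log-normal, median 4 cm², log SD 0.8.
- A share h of ulcers closes to area 0.
- Each remaining area is multiplied by exp(X), with X normal.

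Share of trials with Wilcoxon signed-rank p < 0.05 within one arm:

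| Change in unhealed ulcers | h = 50% | h = 30% | h = 20% |
|---|---|---|---|
| No net change, log SD 0.4 | about 98% | about 59% | about 30% |
| No net change, log SD 0.8 | about 83% | about 34% | about 13% |
| Growth of about 22% (log mean 0.2, exp 0.2 = 1.22), log SD 0.4 | about 67% | about 8% | about 10% |

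Repeat runs move these figures by a few points.

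**5. The between-arm test under the same conditions.** Two identical arms of 42 (median 5 cm², log SD 0.8; unhealed ulcers with no net change, log SD 0.5; 2000 runs):

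| Share closed | Within-arm Wilcoxon significant | Between-arm Mann-Whitney significant |
|---|---|---|
| 20% | 24% | 5.0% |
| 30% | 52% | 5.1% |
| 40% | 81% | 4.3% |
| 50% | 96% | 5.7% |
| 65% | over 99.9% | 5.0% |

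The between-arm test holds its nominal 5% because both arms share the same course. The within-arm rate follows the share closed and the drift of the unhealed ulcers, whatever caused either.

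**The case against.** The strongest reply is that the comparative intent is plain. The summary says so, the introduction names both products, Section 6.1 sizes the trial for a between-arm margin, and 8.2 tests the primary outcome only between arms. Section 8.3 opens by saying that the two arms will be compared and gives every outcome a between-arm test. The within-arm tests are secondary and touch neither sample size nor patients. This stands, and it rules out several stronger readings that a reader might infer:

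- *The trial has no answerable question.* It has one. Only the wording of Section 4 misses it.
- *The primary objective rests on before-after tests.* It does not. Healed status is never tested within an arm.
- *The protocol plans to infer a bandage difference when one arm is significant and the other is not.* No section says so. Section 8.3 assigns that comparison to the Mann-Whitney test. Nor does any section state that within-arm tests will support an efficacy claim.
- *Within-arm tests will almost always be significant.* That depends on the assumptions. If unhealed ulcers grow, the rate at 20% to 30% closure falls to about 8% to 10%. The 50% planning figure is healing under compression; the documents give no closure rate without it. Nothing was calculated for PUSH, pain, pruritus or quality of life.
- *The control's effect is unestablished.* The introduction calls evidence on reduced compression scarce, but it also calls compression the mainstay of treatment. The scarcity remark alone does not carry that conclusion.

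The reply does not remove the mismatch. The governing section still states an objective that the design cannot meet, and 8.3 still prescribes p-values that bear on no question the design can answer.

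**Conclusion.** The point holds in a limited form. Sections 4.1 and 4.2 should pose the comparative question that the summary, Section 6.1 and Section 8.2 already pose. The within-arm Wilcoxon tests on six secondary outcomes carry no evidence on the efficacy of either bandage or of Lite compression. That conclusion follows from the absence of an arm without Lite compression and does not rest on the simulation.

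The simulation only shows how misleading such a p-value can be. For ulcer area, with 20% to 50% closed and identical arms, significance ranges from about 8% to about 98%, against about 5% between arms. The range rests on assumed distributions for baseline size and for change in unhealed ulcers, and should be read as an illustration.

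The stated sample size of 92 and the primary analysis are not affected by this point. What is affected is the set of statements the trial may make at the end.

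**What to change.** - **4.1:** state the objective as whether Andoflex TLC Calamine Lite is non-inferior to Coban 2 Lite in the proportion of index ulcers healed at week 12, with the protocol's 15-point margin.
- **4.2:** state each secondary objective as a comparison of the two bandages on the listed outcome. Align the summary and the introduction.
- **8.3:** drop the within-arm Wilcoxon p-values, report within-arm change as descriptive summaries, and draw conclusions only from the between-arm comparison.
- Add one sentence saying that the trial does not estimate the effect of Lite compression itself.

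Cost: text changes in these sections and fewer tests. Sample size, visits, data and patient care are unchanged. The downside is that a before-after efficacy statement is given up.
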